9.4 Population Sets

9.4.1 Treatment Arm

The "as randomized" treatment arm is defined as the treatment arm allocated at randomization according to the randomization scheme (even if the treatment received is different).

The "as treated" treatment arm also called "actual treatment arm" is defined as the longest duration of treatment received during the 12-week treatment period.

9.4.2 Analysis Sets

Analysis Set	Abbreviation (if applicable)	Definition
Screening Analysis Set		All patients who signed the informed consent and have performed Visit 1 (Screening).
Safety Analysis Set	SAF	All patients, from the Screening Analysis Set, who received at least 1 dose of IMP in the trial. Only patients for whom it has been confirmed that they did not take IMP will be excluded from the Safety Analysis Set, for example where this is reported as a protocol deviation
Full Analysis Set	FAS	All patients from the SAF who signed the informed consent and are randomized by IRT.
Pharmacokinetic Analysis Set	PK Analysis Set	All patients who have received at least 1 dose of nabiximols and provided sufficient bioanalytical data to calculate reliable (based on the judgement of the pharmacokineticist) estimates of the PK parameters of THC, CBD, and their metabolites. For the purposes of biostatistics and programming team this will be patients who have taken at least one dose of nabiximols and have at least one PK parameter concentration and will be determined post unblinding; The final PK population being defined by the pharmacokineticist.

Table 9.4-1 Analysis Set Definitions and Abbreviations

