#### SPONSOR: GW PHARMA LIMITED

## Table 2-1

#### **Objectives and Endpoints**

### **Primary Estimand:**

The primary estimand for this study is defined by the following 3 components:

- Target population: patients with spasticity due to MS who have not achieved adequate relief from other antispasticity agents but have optimized treatment
- Endpoint: change from baseline in average daily spasm frequency count (from Days 57 to 84 compared to the average daily spasm count for the baseline period)
- Measure of intervention effect: mean difference in change from baseline between patients randomized to nabiximols compared to patients randomized to placebo, regardless of treatment compliance and change of other antispasticity medications; following a treatment policy strategy for handling intercurrent events.

All randomized patients and all measurements collected after treatment discontinuation and after change in antispasticity medication will be included in the primary analysis.

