#### Full Analysis Set

- All patients who sign the informed consent, and are randomized will be included and analyzed according to their randomized treatment arm
- The full analysis set (FAS) is the primary analysis set for all efficacy endpoints

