# 13.6.1 Primary Endpoint

The primary endpoint is the change from baseline in average daily spasm count (the average daily spasm count from Days 57 to 84 compared to the average daily spasm count for the baseline period) for all randomized patients regardless of treatment compliance.

The average daily spasm count will be calculated for the baseline period and each 28-day period corresponding to Days 1 to 28, Days 29 to 56, and Days 57 to 84. The change from baseline for average daily spasm count will be calculated for Days 1 to 28, Days 29 to 56, and Days 57 to 84.

Average daily spasm count for each period is defined as follows:

Total spasm count for the period Number of days in which the daily diary was completed during the period

For post-randomization data, the average daily spasm count over the 28-day period will only be calculated if there are  $\geq 15$  days of non-missing data and < 10 consecutive days of missing data. If there are < 15 days of non-missing data or  $\geq 10$  consecutive days of missing data then the average daily spasm count for the 28-day period will be set to missing.

The average daily spasm count and change from baseline will be summarized by treatment for each 28-day period.

The change from baseline will be analyzed using mixed model repeated measures (MMRM), using data for each 28-day period. The model will include baseline average daily spasm count, prior cannabis use, region (US versus non-US), period, treatment arm,

period by treatment arm interaction, and period by baseline interaction as fixed effects. Period repeated within each patient will be included as a repeated effect. Denominator degrees of freedom adjustment will be performed using the Kenward-Roger method.

The within-patient correlation structure will be modelled using an unstructured covariance matrix. If the model does not converge the following structures will be used in order of preference Toeplitz, first-order autoregressive and Compound symmetry.

The least squares mean estimates for each treatment arm and period, along with the standard error and 95% confidence intervals (CIs), will be presented. In addition, estimates of the treatment difference at each period in change from baseline will be presented along with standard errors of the difference and 95% CIs. The primary comparison is the estimate of the treatment difference for the Days 57 to 84 period.

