12.1 Patient Disposition

All patient disposition outputs will be based on the FAS unless otherwise stated.

The number and percentage of patients screened, rescreened, randomized and not randomized along with reason of screen failure will be presented using the Screening analysis set.

The number of patients randomized, randomized and treated, randomized and not treated, and the number of patients in the analysis sets will be summarized per treatment arm.

The number and percentage of patients will also be summarized per treatment arm for the following patient disposition categories:

- Completed the study
 - Completed treatment phase,
 - Discontinued IMP early and the reason for discontinuation,
- Discontinued from the study early and the reason for discontinuation,
- Completed the follow-up visit.

Descriptive statistics for time in study (as detailed in Section 10.8) will be provided by treatment arm.

Summaries of patient disposition will be repeated for the different subgroups presented in Table 9.3-1.

A tabulation of the number and percentage of patients randomized at each center will be presented by country per treatment arm and overall.

The number and percentage of randomized patients will also be summarized by randomization strata as recorded by the IRT. Additionally, a description of each randomization strata will be presented by the strata entered into the eCRF (representing the actual stratification factor in case of mis-stratification) and overall.

The number and percentage of randomized patients attending each scheduled visit will be summarized by treatment arm and overall.

All patient's disposition data will be listed, including membership of analysis sets...

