13	Exclusion criteria	Did not respond adequately to treatment with nabiximols or another cannabis-based medication if exposed at any time before the 30-day period prior to Visit 1.
14*	Exclusion criteria*	Has any other clinically significant disease or disorder (including seizure disorder) that, in the opinion of the investigator, may put the patient, other patients, or site staff at risk because of participation in the trial, influence the interpretation of trial results, or may affect the patient's ability to take part in the trial.
		For certain disorders, determined with medical monitor
15	Study drug	Patient failing to acknowledge in the mobile health platform (MHP) that they have taken at least one spray on 4 or more days out of any 7 consecutive days within days 57 to 84.
16	Study drug	Patient randomized but not exposed to study drug
17	Study drug	Patients exposed outside of randomization call to IRT.
18	Study drug	Patient receiving a kit number which is not the treatment he/she was allocated to by IRT.
19	Efficacy endpoint data	Missing evaluable average daily spasm count pre-dose assessment
20	Efficacy endpoint data	Missing evaluable post baseline average daily spasm count assessment
21	Efficacy endpoint data	Missing evaluable on-treatment Day 85 (between Day 57 and Day 85) average daily spasm count assessment
22	Prohibited medication	Patient taking antipsychotic medication at any time during the trial.
23	Prohibited medication	Patient taking benzodiazepine on an as needed (PRN) basis during the trial
24	Prohibited medication	Patient taking commercial cannabis or any cannabinoid medication during the trial.
25	Prohibited medication	Patient taking botulinum injection during the trial
26	Prohibited medication	Initiation or changes in the dose of MS disease modifying therapy any time after randomization at Visit 2
27	Prohibited medication	Initiation of a new course of physiotherapy any time after Visit 1
28	Prohibited medication	Patient taking drugs solely metabolized by UGT1A9 and UGT2B7 during the trial
29	Prohibited medication	Patient taking strong CYP3A4 inducer or inhibitor during the trial
30	Prohibited medication	Patient changing dose or introducing antispasticity medication (baclofen, tizanidine, dantrolene)
31	Prohibited medication	Patient changing dose or introducing dalfampridine or fampridine
32	Randomization irregularities	Deviation description with regards to randomization specification

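### The SAP builds the Full Analysis Set from dosed patients only, although the protocol's FAS and primary estimand cover all randomized patients

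*SAP*

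**What the plan says.** **Protocol.** Section 13.3 defines the FAS without any dosing condition: "All patients who sign the informed consent, and are randomized will be included and analyzed according to their randomized treatment arm". It adds: "The full analysis set (FAS) is the primary analysis set for all efficacy endpoints". The primary estimand in Table 2-1 uses a treatment policy strategy and states: "All randomized patients and all measurements collected after treatment discontinuation and after change in antispasticity medication will be included in the primary analysis". Section 13.6.1 defines the primary endpoint "for all randomized patients regardless of treatment compliance". The dose condition appears only in the definition of the Safety Analysis Set.

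**SAP.** Table 9.4-1 (section 9.4.2) defines the FAS as "All patients from the SAF who signed the informed consent and are randomized by IRT". The parent set, the SAF, consists of screened patients "who received at least 1 dose of IMP in the trial", and it leaves out those confirmed not to have taken study drug. Section 9.1 gives the FAS as the population of both the primary and the secondary estimand. Sections 12.5.2.1 and 12.5.3.1 run the spasm-count and MSSS-88 models on it. Section 6.2 lists no changes from the protocol.

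**Addendum.** Section 7.0 and Table 7-1 keep the primary and secondary inferential analyses as the SAP describes them, drop the sensitivity and supplemental analyses, and do not touch the FAS definition.

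**The concern.** By nesting the FAS in the SAF, the SAP turns a set fixed at randomization into one that depends on what happened afterwards. A treatment policy estimand for all randomized patients counts never starting treatment as part of the outcome of assignment. Removing those patients answers a different question. Because the SAP also writes its FAS into the estimand population, the estimand itself is altered, and nothing tells the reader so.

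The situation can arise. Randomization takes place on the morning of Day 1 (SAP 8.3), and the first spray is self-administered that evening (Protocol 9.1.2). Patients who are off study drug are asked to stay in the trial and keep up the diary (Protocol 4.1). An undosed patient who does so can supply evaluable 28-day averages, because the analysis periods run from randomization (SAP 10.2.1 and 10.2.2). The SAP's FAS would discard that data. With the addendum in force, no all-randomized analysis remains to show whether the exclusion mattered.

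**Working it through.** **1. The definitions side by side**

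| Item | Protocol | SAP |
|---|---|---|
| FAS | consented and randomized (13.3) | consented, randomized and in the SAF (Table 9.4-1) |
| Dosing condition on the FAS | none | at least one dose; confirmed non-takers removed |
| Primary estimand population | all randomized (Table 2-1, 13.6.1) | patients in the SAP's FAS (9.1) |
| Declared change | not applicable | none (6.2) |

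The two sets differ by exactly the randomized patients confirmed never to have taken study drug.

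**2. Consistency within the SAP**

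- Section 12.1 bases disposition on the FAS unless otherwise stated, yet it asks for "The number of patients randomized, randomized and treated, randomized and not treated". Read literally on the SAP's FAS, the last of these counts is always zero.
- Table 12.4-2, item 16, "Patient randomized but not exposed to study drug", is a major deviation that excludes a patient from the per-protocol set. That set is a subset of the FAS (Table 9.4-2), which no longer contains such patients, so the item excludes nobody.

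Both provisions make sense only if the FAS is all randomized patients.

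**3. The plan's own sample size figure**

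Inputs from Protocol 13.1: difference 2, SD 6.5, two-sided 5%, 90% power, 223 per arm.

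- n per arm = 2 × (1.960 + 1.2816)² × 6.5² / 2² = 222, or 444 in total, by the normal approximation.
- Power at 223 per arm = Φ(2 / (6.5 × √(2/223)) − 1.960) = 0.9013.
- With the noncentral t distribution, power is 0.8988 at 222 and 0.9001 at 223 per arm, which gives the stated 446.

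The planned figure is reproduced, and it does not change with the FAS definition.

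**4. Possible size of the exclusion**

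The documents give no rate of randomized but undosed patients, so a share f is assumed, equal in both arms.

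- Patients removed = 446 × f.
- Dosed-only power uses 223 × (1 − f) per arm and a difference of 2.
- All-randomized power uses 223 per arm and a difference of 2 × (1 − f). This supposes that undosed patients supply data, show no treatment effect and leave the SD unchanged.

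| f (assumed) | Removed | Power, dosed only | Difference, all randomized | Power, all randomized |
|---|---|---|---|---|
| 1% | 4.5 | 0.8985 | 1.98 | 0.8955 |
| 2% | 8.9 | 0.8955 | 1.96 | 0.8895 |
| 3% | 13.4 | 0.8925 | 1.94 | 0.8833 |
| 5% | 22.3 | 0.8862 | 1.90 | 0.8700 |

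The power gap between the definitions is 0.8925 − 0.8833 = 0.0092 at 3%, and 0.8862 − 0.8700 = 0.0162 at 5%. Under these assumptions, leaving out undosed patients makes the estimated difference larger.

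**The case against.** The strongest case on the other side is that the exclusion is narrow and unlikely to move the result. Only confirmed non-takers leave; the SAP takes the start date from dispensing (10.1), so a patient with unknown intake stays in. The trial is double-blind with matching placebo and the first dose is due on the evening of randomization, so a failure to start comes before any experience of treatment and no mechanism linked to arm is apparent. An undosed patient who stops the diary has no post-baseline average and adds nothing to the model under either definition (SAP 10.5). The assumed 1-3% has no anchor in the documents, and it is applied to 446 although recruitment stopped early. The disposition row can be read as naming its own population, and the addendum drops the summaries of major deviations.

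All of this stands as a limit on size, and the internal inconsistencies are supporting evidence only. None of it reconciles the two definitions or supplies the missing declaration. Early stopping also works the other way, since each exclusion is then a larger share of a smaller sample.

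A further objection is practical. For confirmed non-takers the treatment start date is set to missing (SAP 10.1), and the clinic baseline rule in SAP 10.4.2 refers to that date, so restoring these patients could leave their MSSS-88 baseline undefined. SAP Table 10.2-1 largely answers this, because it ties the MSSS-88 baseline window to the randomization date. The diary baseline is unaffected.

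**Conclusion.** The concern holds. The SAP's FAS is all randomized patients less the confirmed non-takers, whereas the protocol specifies all randomized patients for the FAS, the primary endpoint and the estimand. The protocol does not use the term intention-to-treat, but its text amounts to that. Both confirmatory analyses are affected, the change is undeclared, and the addendum carries it forward.

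The numerical effect is probably small: about 4 to 13 patients at an assumed 1-3% of 446, with less than 0.01 in planned power between the definitions. Those figures rest on an assumed rate, the planned sample size, and no treatment effect in undosed patients. The point should nevertheless be corrected before unblinding, because it concerns which patients the confirmatory result describes, and the correction is nearly free.

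**What to change.** In SAP Table 9.4-1, remove the condition that FAS members come from the SAF. Define the FAS as all patients who signed informed consent and were randomized by IRT, analysed in their randomized arm whether or not they took study drug. Leave the SAF definition unchanged. The disposition counts in 12.1, the per-protocol subset in Table 9.4-2 and item 16 of Table 12.4-2 then agree with the FAS as they stand. A line in SAP 10.4.2 stating that the clinic baseline is taken before randomization when the treatment start date is missing would remove any doubt about MSSS-88. Because the addendum relies on the SAP definition, the correction should be cited there too.

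The cost is SAP wording and one population flag. The estimate may be slightly diluted if undosed patients supply data, which is what the stated estimand calls for. If the sponsor prefers the dosed set, the minimum is to declare and justify the change in SAP 6.2 and to add the primary analysis on all randomized patients.

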9.4.3 Subsets

Table 9.4-2 Subset Definitions and Abbreviations

Analysia	Abbreviation	Definition
Set	(if applicable)	
Per Protocol Analysis Set	PP Analysis Set	Subset of the FAS that includes all patients who have completed the trial with no major important protocol deviations deemed to compromise the assessment of efficacy. Major protocol deviations will be identified as a subset of the important protocol deviation and fully defined prior to unblinding of the trial.
Follow-up Analysis Set	FUAS	Subset of the FAS that includes all patients who have completed Week 12 on-treatment and have follow-up data.

10.0 Conventions and Derivations

10.1 Source of Key Dates

- The IMP Start Date will be assumed to be the first date of IMP dispense, which will be obtained from the IRT data. If there is documented confirmation that patient did not take IMP eg where this is reported as a protocol deviation, the IMP Start Date will be set to missing.
- The IMP End Date will be taken from eCRF "End of treatment" form.
- The Last Day in Study will be taken from "Study Completion/Discontinuation Date" on the "End of study" form for patients that completed or discontinued early for any reason other than Lost to Follow-up. For patients Lost to Follow-up, the Last Day in Study will be their last contact date.

10.2 Reference Day, Study Day, Study Periods and Analysis Visit Window

10.2.1 Reference Day and Study Day

The reference day (Study Day 1) will be the date of randomization. However, in the event that IMP is dispensed before randomization first date of IMP dispense will be used (see Section 10.1).

The study day is defined relative to the reference day date.

- For assessments that occur on or after this date, the study day will be calculated as assessment date reference day date +1.
- For assessment that occur prior to the reference day date, the study day will be calculated as assessment date reference day date.

Thus, there is no study day referring to Day 0.

10.2.2 Study Periods

The following study periods will be defined:

. . .

- Screening/baseline period: starting the day of the informed consent signature and ending
 - For clinical based endpoints: on Day 1 (as defined in Section 10.2.1) before first IMP intake
 - For eDiary based endpoints: the day prior to Day 1
- **12-week randomized period:** starting on Day 1 (as defined in Section 10.2.1) and ending the day of Visit 6 (end of treatment or early withdrawal visit).
 - For the eDiary endpoints of spasm count and NRS spasm severity this period will be split into three 4-week periods:
 - Week 1 to 4; defined as Day 1 to Day 28
 - Week 5 to 8; defined as Day 29 to Day 56
 - Week 9 to 12; defined as Day 57 to Day 84
 - For the eDiary endpoint of NRS spasticity this period will be split into twelve 1-week periods:
 - Week 1; defined as Day 1 to Day 7
 - Week 2; defined as Day 8 to Day 14
 - Week 3; defined as Day 15 to Day 21
 - Week 12; defined as Day 78 to Day 84
- **12-week on-treatment period**: which starts on the IMP Start Date and ends on the IMP End Date(+ x days), where x will be equal to 30 days for safety assessment and medication, and 0 days for efficacy. See Section 10.1 for definitions of IMP Start Date and IMP End Date.

- For IMP dosing summaries this period will be considered as follows:
 - The titration period; defined as Day 1 to Day 14
 - The maintenance period; defined as Day 15 to IMP End Date
 - On-treatment period; defined as Day 1 to IMP End Date
- **Follow-up period:** for eDiary based endpoints this starts on the day after IMP End Date and ends 14 days after IMP End Date.
 - For the eDiary endpoint of NRS spasticity this period will be split into two 1-week periods:
 - Follow-up Week 1; defined as the day after IMP End Date to the day 7 days after IMP End (inclusive)
 - Follow-up Week 2; defined as the day 8 days after IMP End Date to the day 14 days after IMP End Date (inclusive)
- Follow-up baseline period: the baseline period for the follow-up analysis for eDiary based endpoints starts 13 days before IMP End Date and ends on IMP End Date, ie covers a 14-day period ending on IMP End Date.

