# 9.1.4 Visit 6 (Day 85, End of Treatment Visit/Withdrawal Visit)

This visit will occur 84 days after the first dose of IMP or earlier, if the patient withdraws from the trial. A visit window of  $\pm$  7 days from the scheduled visit date is permitted, but it is preferred that the visit is performed on the scheduled visit day, where possible.

Patients who discontinue IMP treatment early will be encouraged to continue (off treatment) in the trial and to complete all remaining trial procedures to Visit 6 (Day 85), where possible.

The following assessments/procedures will be performed:

- Concomitant medications review
- AE review
- Physical and oral mucosa examinations
- Body weight measurement
- Vital signs measurement
- 12-lead ECG
- Clinical laboratory blood sampling (hematology and biochemistry)
- PK blood sampling (see Section 9.2.12.1)
- Dipstick urinalysis
- Serum pregnancy test (if appropriate)
- MSSS-88 assessment
- C-SSRS assessment
- T25FW test

V1, 24Sep15

- Medication Use Survey (MUS [Section 9.2.15.5])
- SF-36 assessment
- IMP collection and compliance review

Patients should be reminded to record their spasm count, 11-point NRS spasm severity score, 11-point NRS spasticity score, and use of antispasticity medications in the electronic diary once daily, around the same time of the day, preferably in the evening before retiring to sleep.

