# 9.1.5 Visit 7 (Day 99, Safety Follow-up Visit)

The Safety Follow-up Visit will occur 14 days after the End of Treatment Visit or Withdrawal Visit. A visit window of  $\pm 4$  days from the scheduled visit date is permitted, but it is preferred that the visit is performed on the scheduled visit day, where possible. Patients who discontinue IMP but complete scheduled trial visits are not required to complete the Safety Follow-up Visit.

The following assessments/procedures will be performed:

- Concomitant medications review
- AE review
- Vital signs measurement

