# SPONSOR: GW PHARMA LIMITED

# 9.2.14 Electronic Patient Diary

As part of the baseline period, patients will record their spasm count, 11-point NRS spasm severity score, 11-point NRS spasticity score, and use of antispasticity medications in the electronic diary once daily, around the same time each day, during the baseline period prior to Visit 2 and throughout the trial until Visit 7, unless otherwise indicated. Patients are expected to start completing their electronic diary in the evening of their screening visit (first day of the 28-day baseline period).

In addition, on the day before PK blood sampling, patients will be prompted to record whether they started their morning and evening doses of IMP within 30 minutes of a meal.

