# 13.1 Sample Size, Power, and Significance Levels

446 patients will be randomized to the nabiximols or placebo treatment arms on a 1:1 basis.

The following assumptions have been used for the sample size:

- Common standard deviation of 6.5 for the change from baseline in average daily spasm count for nabiximols and placebo treatment arms
- True mean difference of -2 between the mean change from baseline in average daily spasm count in the nabiximols treatment arm compared to the placebo treatment arm

Using the above assumptions, the total sample size of 446 patients (223 patients per treatment arm) will have 90% power to detect a difference between treatment arms in change from baseline in average spasm count of -2 using a 2-sided hypothesis test at the 5% significance level.

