12.5 Efficacy Analyses

All efficacy analyses, unless otherwise specified, will be performed on the FAS during the 12-Week randomized period (as defined in Section 10.2.2) regardless of treatment compliance and permanent treatment discontinuation.

To assess robustness of the results with regards to intercurrent events some analyses may be repeated, for instance:

- During the 12-week on-treatment period (as defined in Section 10.2.2), using only on-treatment assessments,
- During the 12-week randomized period (as defined in Section 10.2.2), using the PP analysis set,
- During the 12-week randomized period excluding patients having at least one missing assessment due to COVID-19.

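### SAP 10.2.2 conflicts with itself on diary entries after an early withdrawal visit; if its stated end date is applied, counts that the treatment-policy estimand calls for leave the primary analysis

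*SAP*

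**What the plan says.** **The estimand.** Protocol Table 2-1 sets a treatment policy strategy for all randomized patients and says that "all measurements collected after treatment discontinuation and after change in antispasticity medication will be included in the primary analysis". SAP Table 9.1-1 likewise keeps every observed value, whatever intercurrent event has occurred.

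**The analysis period.** SAP 10.2.2 starts the 12-week randomized period on Day 1 and describes it as "ending the day of Visit 6 (end of treatment or early withdrawal visit". The same bullet then splits that period, for spasm count and NRS spasm severity, into Days 1-28, 29-56 and 57-84, and for NRS spasticity into twelve 1-week windows. SAP 10.17 derives the averages for the three 4-week periods within the randomized period. SAP 12.5 has efficacy analyses "performed on the FAS during the 12-Week randomized period (as defined in Section 10.2.2) regardless of treatment compliance and permanent treatment discontinuation". Protocol 13.6.1 uses the same 28-day windows and mentions no cut at withdrawal.

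**The data collected.** The diary is kept "during the baseline period prior to Visit 2 and throughout the trial until Visit 7, unless otherwise indicated" (Protocol 9.2.14). Protocol 9.1.4, which covers both the scheduled Visit 6 and the withdrawal visit, says: "Patients should be reminded to record their spasm count, 11-point NRS spasm severity score". Protocol 9.1.5 adds: "The Safety Follow-up Visit will occur 14 days after the End of Treatment Visit or Withdrawal Visit", with a window of ±4 days. Appendix 1 asks for no entry on the day of Visit 7 itself, so the last planned diary day is the day before.

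**The follow-up analysis.** The FUAS in SAP 9.4.3 is limited to "all patients who have completed Week 12 on-treatment and have follow-up data", so it does not pick up the diary days of early withdrawers.

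**The concern.** The parent bullet in SAP 10.2.2 closes the period at the early withdrawal visit, while its sub-bullets run on fixed study days. For a patient whose withdrawal visit falls inside a 28-day window, the two give different data. The SAP does not say which prevails.

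If the parent end date is applied, as SAP 10.17 and 12.5 imply, up to about two weeks of planned counts after each early withdrawal visit are left out. These are off-drug outcomes in patients who stopped treatment, the kind of data a treatment-policy estimand is meant to keep. Without them, the MMRM's missing-at-random assumption models these patients on those who stayed, most of whom are presumably still on drug. If early withdrawers have lost drug benefit, the estimate moves in favour of nabiximols relative to the stated estimand.

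No remaining analysis would show this. The placebo-based imputation in SAP 12.5.2.2 would have covered patients with a baseline but no post-baseline average. The SAP addendum (Section 7.0, Table 7-1) keeps the primary test and cancels the sensitivity and supplemental analyses.

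**Working it through.** **1. The plan's own figure.** Protocol 13.1 assumes a difference of -2 and an SD of 6.5, "using a 2-sided hypothesis test at the 5% significance level", with 90% power. The normal formula gives n per arm = 2(1.960 + 1.282)² × 6.5² / 2² ≈ 222. The noncentral-t calculation gives power 0.8988 at 222 and 0.9001 at 223 per arm, so 223 (446 in total) is reproduced. The sample size is not in dispute; the -2 is used in step 5.

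**2. Set-up.** Let w be the study day of the early withdrawal visit, with the diary complete until it stops. Compare a diary cut at w with one kept to w + 13, the day before a Visit 7 held 14 days later. The two documents state different missing-data rules, so both are carried:
- Protocol 13.6.1: the average is missing if there are fewer than 15 observed days **or** at least 10 consecutive missing days.
- SAP 10.17: it is missing if there are fewer than 15 observed days **and** at least 10 consecutive missing days.

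**3. Evaluability of Days 1-28.** If the last diary day is L (at most 28), there are L observed days and 28 - L trailing missing days.
- Protocol rule: needs L ≥ 15 and 28 - L < 10, so L ≥ 19. With the cut, w ≥ 19. With the diary kept, w + 13 ≥ 19, so w ≥ 6. The cut loses the average for w = 6-18.
- SAP rule: needs L ≥ 15, or 28 - L < 10 (already implied by L ≥ 19), so L ≥ 15. With the cut, w ≥ 15. With the diary kept, w ≥ 2. The cut loses the average for w = 2-14.

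Adding 28 and 56 days gives the other windows:

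| Average | Lost by the cut, protocol rule | Lost by the cut, SAP rule |
|---|---|---|
| Week 1-4 | Days 6-18 | Days 2-14 |
| Week 5-8 | Days 34-46 | Days 30-42 |
| Week 9-12 (primary) | Days 62-74 | Days 58-70 |

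Example at the primary timepoint: with a visit on Day 66, the cut leaves Days 57-66, which is 10 observed and 18 missing days, not evaluable under either rule. Kept to Day 79, there are 23 observed and 5 missing days, evaluable under both.

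Each set covers 3 × 13 = 39 of the 83 possible visit days from Day 2 to Day 84 (47%). Only 13 of 83 (16%) concern Week 9-12. These are shares of days; they are shares of patients only if withdrawal visits are spread evenly, which the documents do not say. With Visit 7 at 10 instead of 14 days, each range starts four days later; at 18 days, four days earlier (but not before Day 1).

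**4. Who loses every post-baseline value.** With the cut, this needs a visit on or before Day 14 (SAP rule) or Day 18 (protocol rule). Over visit days from Day 2, keeping the diary reduces the days with no post-baseline value from 13 to 0 (SAP rule) or from 17 to 4 (protocol rule: Days 2-5 remain). For a visit by Day 18, the diary ends by Day 18 + 13 = 31, so only the Week 1-4 average can be restored.

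**5. Bias, as a scenario only.** Assume a fraction q of the nabiximols arm is lost this way, has no off-drug effect, and that those who stay have an effect of -2. None of this is in the documents.
- Treatment-policy effect: -2(1 - q). The cut analysis returns about -2. The overstatement is 2q: 0.10, 0.20, 0.30 and 0.40 spasms/day for q = 5, 10, 15 and 20%.
- With the Week 1-4 average restored, a large-sample MMRM with correlation ρ between Week 1-4 and Week 9-12 (equal variances) and a Week 1-4 on-drug effect e₁ has bias -2q + ρq|e₁|. At q = 10%, ρ = 0.5 and e₁ = -1 give -0.20 + 0.05 = -0.15; ρ = 0.8 and e₁ = -2 give -0.20 + 0.16 = -0.04. The fix removes 25% to 80% of the scenario bias.

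**The case against.** **The cut is only one reading.** The sub-bullets of SAP 10.2.2 are fixed study days, Protocol 13.6.1 agrees with them, SAP 12.5.2.1 takes all available post-baseline averages, and SAP 6.2 declares no change from the protocol. A Visit 6 on Day 92, within its ±7-day window, would not extend Week 9-12 past Day 84, so the parent end date does not by itself set the windows. This stands. A reader might infer that the SAP definitely discards these counts; the text shows only that it contains both rules and does not choose. The confirmatory derivation still depends on the choice.

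**The data may not exist.** Protocol 4.1 reserves the Early Withdrawal Visit for patients unwilling or unable to follow the schedule and its requirements, with diary entry given as an example of those requirements. They may well stop the diary. The reminder in Protocol 9.1.4 is one list for both kinds of Visit 6, and SAP Table 10.2-1 expects the follow-up visit 10 to 14 days after early withdrawal, so w + 13 is the upper end there. This also stands. Entry to Visit 7 is planned, but the ranges above are the most the cut could cost with Visit 7 at 14 days.

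**Most discontinuers are not touched.** Patients who stop IMP but stay on the visit schedule continue to Day 85, and the cut does not reach them. A reader might infer that all post-discontinuation data are at risk, or that everyone who stops during titration leaves the model. Neither follows. The visit may come up to 14 days after the last dose: stopping on Day 10 with a visit on Day 24 leaves 24 observed days, evaluable under both rules even with the cut.

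**Conclusion.** Wrong as written. SAP 10.2.2 gives two incompatible rules for diary days after an early withdrawal visit, and the one that SAP 10.17 and 12.5 point to excludes counts that the estimand says are used.

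The ranges of affected visit days are firm arithmetic, given a complete diary and a Visit 7 at 14 days. The direct effect on the primary timepoint is confined to withdrawal visits on Days 62-74 (protocol rule) or 58-70 (SAP rule). Earlier withdrawals affect it only indirectly, through the correlation between periods.

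The size of any bias is unknown. The 0.1-0.4 spasms/day, 5% to 20% of the assumed effect of 2, is a scenario resting on an assumed withdrawal rate, no off-drug effect and an assumed effect of -2 among those who stay. Protocol 13.1 states -2 as the true difference between arms and does not call it an on-drug effect. A reader might take these figures as an expected bias of 10% or more; the documents do not support that.

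The point should still be settled before unblinding, because the primary hypothesis is still to be tested and the analyses that might have revealed the effect have been dropped.

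**What to change.** Add to SAP 10.2.2, or to the addendum: *For eDiary endpoints the fixed study-day windows govern. All diary entries recorded in Days 1-28, 29-56 and 57-84 (and in each 1-week window for NRS spasticity) are used, including entries made after an early withdrawal visit up to the day before Visit 7. The end of the period at Visit 6 applies to clinic-visit endpoints only.*

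The same sentence would settle the separate case of a completer whose scheduled Visit 6 falls before Day 84 (the ±7-day window allows Day 78), so the sponsor should confirm that this is intended.

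The cost is one sentence and a changed date filter in the diary derivation, with no new data collection. Some averages will mix on- and off-drug days, as a treatment-policy estimand accepts, and the estimate may be slightly less favourable to nabiximols. The change restores only what patients actually entered, and for visits by Day 18 at most the Week 1-4 value, so it reduces the problem without removing it.
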